  - 8.6.3. **Intervention 2 Description:** Participants consumed a placebo consisting of encapsulated high-oleic safflower oil. Each placebo capsule contains 866.9 mg/capsule active ingredient. The placebo intervention included consumption of 6 capsules 5 days a week for 25 weeks. A certificate of analysis confirming manufacture date (06/03/2019), active ingredient (safflower oil), fill weight (866.9 milligrams), and microbiology safety (all negative), and disintegration time (3 minutes) was provided.
- 8.7. **Arm/Intervention Cross-Reference:** Arm 1 = Intervention 1; Arm 2 = Intervention 2
- 9. Outcome Measures
  - 9.1. Outcome 1: Primary Outcome Measure
    - 9.1.1. **Title 1:** The effect of DHA and EPA Omega-3 PUFA fish oil supplementation on blood biomarkers of brain injury compared to placebo (high-oleic safflower oil) over a course of

Study Title: Study of Effect of Docosahexaenoic Acid (DHA) and Eicosapentaenoic acid (EPA) on Biomarkers of Sub-concussion Injuries in American Football.

IRB #: 1904553365

the American football season among collegiate football athletes exposed to repeated subconcussive head impacts.

- 9.1.2. **Time Frame 1:** 32 weeks from baseline to one month postseason/treatment
- 9.1.3. **Description 1:** (not required) Blood-based biomarkers for sub-concussion injury (neurofilament light (NFL), Tau protein (Tau), ubiquinone C-terminal hydrolase L1 (UCH-L1)) and can lower inflammatory cytokines (C-reactive protein (CRP), tumor necrosis factor 1 (TNF-α), interleukin 6 (IL6)) will be measured at baseline, mid-treatment, post treatment, and one month (recovery) after the end of treatment and the football season.

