### 9.2. Outcome 2: Primary Outcome Measure

- 9.2.1. **Title 2:** The effect of DHA and EPA Omega-3 PUFA fish oil supplementation on blood cholesterol, low-density lipoprotein (LDL), high-density lipoprotein (HDL), and triglyceride levels in collegiate football athletes.
- 9.2.2. **Time Frame 2:** 25 weeks from baseline to end of treatment
- 9.2.3. **Description 2:** (not required) A lipid panel will be assessed at baseline and end of treatment.

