# Power, Sample size, and Confidence intervals

This study is both an independent replication of a previous omega-3 supplementation trial with college football players, as well as an exploratory, hypothesis-generating extension that will collect additional biological data including cardiometabolic biomarkers and untargeted lipidomics. For statistical power, our primary hypothesis-driven question is whether DHA+EPA supplementation will have a protective or restorative effect based on measured levels of markers of neuronal damage, such as NFL, and whether this will vary by starter/non-starter. In this study, with a samples size of n=44 starters, n=44 non-starters, and a significance level of  $\alpha$ =0.05, we have 80% power to detect an effect size of d = 0.6, where d=( $\mu_1 - \mu_2$ )/ $\sigma$ , is the difference in the group means divided by the pooled standard deviation. The TCU study looked at the differences between starters and non-starters at multiple time points and found effect sizes ranging from 0.88 to 2.07. The TCU study also found dramatic changes in NFL levels between starters on placebo, with levels more than doubling over the season, while starters on supplementation saw a more modest increase of 35% by the end of the season. If we look only at starters, and compare the supplement (n=22) and placebo groups (n=22), we are powered to see an effect size of 0.86, well below the reported differences at many time points in the TCU study. We anticipate some other biomarkers will also change over time, and we are

well-powered to detect small to moderate effects. For previously unstudied biomarkers, our focus will be on estimating the magnitude and direction of effects in order to discover which are the most informative as markers of brain injury/recovery or omega-3 supplementation.

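### The SAP's claim of good power for small to moderate effects has no calculation behind it: small supplement effects are out of reach even at 88 players, and at the 38 enrolled moderate ones are too unless within-person correlation is high

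*SAP*

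**What the plan says.** All the power statements are in the SAP under Power, Sample size, and Confidence intervals.

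- With 44 starters and 44 non-starters at a significance level of 0.05, "we have 80% power to detect an effect size of d = 0.6".
- For starters only, 22 on supplement against 22 on placebo, "we are powered to see an effect size of 0.86, well below the reported differences at many time points in the TCU study".
- Other biomarkers are then expected to change over time, and the study is called "well-powered to detect small to moderate effects". The biomarkers are not named, small and moderate are not defined, and no effect size, correlation or calculation is given.
- The next sentence reads: "For previously unstudied biomarkers, our focus will be on estimating the magnitude and direction of effects".

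The SAP's Study Randomization section presents 44 + 44 as the number the roster could yield. Protocol sections 7.4, 7.9 and 7.10 give 1:1 allocation and an actual enrolment of 38.

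The SAP's list of continuous outcomes includes TNF-a, IL-6 and the lipid panel, all to be analysed with a longitudinal mixed model. Protocol section 9.1 puts TNF-α and IL6 under a primary outcome, measured at baseline and at three later points. The lipid panel is also primary ("Outcome 2: Primary Outcome Measure"), with a single follow-up: "A lipid panel will be assessed at baseline and end of treatment".

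**The concern.** A detectable size of 0.6 SD lies above what is usually called moderate and far above what is usually called small. The two detectable sizes the SAP gives therefore do not support the sentence that follows them, and nothing else in the SAP does.

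What is at stake is interpretation. A reader who takes the sentence at its word could treat a non-significant lipid or cytokine result as evidence that the supplement has no small or moderate effect. With 38 players the data could not show that. The SAP's one safeguard, its focus on estimation, is worded for previously unstudied biomarkers, and it is not clear whether lipids, TNF-a and IL-6 belong to that group.

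**Working it through.** **Inputs.** Alpha 0.05 and 80% power (SAP). The SAP does not state sidedness; two-sided is used because it reproduces the SAP's figures, while one-sided would give 0.53 and 0.76. Group sizes are 44 vs 44 and 22 vs 22 (SAP) and 19 vs 19 (38 enrolled at 1:1; the actual split is not given). Assumed: small = 0.2 SD, moderate = 0.5 SD, no dropout, no multiplicity adjustment.

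**Step 1: reproduce the SAP's figures.** Normal approximation: d = (1.960 + 0.842) × √(2/n).

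- n = 44: 2.802 × 0.2132 = 0.597; noncentral t, 0.604. The SAP says 0.6.
- n = 22: 2.802 × 0.3015 = 0.845; noncentral t, 0.865. The SAP says 0.86.

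Both are correct. The first names starters and non-starters as its groups; it applies to supplement against placebo only if all 88 are split 44/44.

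**Step 2: unadjusted comparison of arms (noncentral t).**

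| Per arm | Detectable d | Power at 0.2 | Power at 0.5 |
|---|---|---|---|
| 44 | 0.60 | 15% | 64% |
| 19 | 0.93 | 9% | 32% |

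At 80% power, 0.5 SD needs about 64 per arm and 0.2 SD about 394.

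**Step 3: allow for the mixed model.** The SAP gives no within-person correlation r, so 0.5 and 0.7 are assumed.

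- One follow-up adjusted for baseline (lipids): multiply by √(1 − r²), which is 0.866 or 0.714.
- Three follow-ups, equal correlation, same arm difference at each visit: multiply by √((1 + 2r)/3 − r²), which is 0.645 or 0.557. This includes the recovery visit after dosing has ended, so it is favourable.

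| Detectable arm difference (SD) | r = 0.5 | r = 0.7 |
|---|---|---|
| Lipids, 88 | 0.604 × 0.866 = 0.52 | 0.604 × 0.714 = 0.43 |
| Three follow-ups, 88 | 0.604 × 0.645 = 0.39 | 0.604 × 0.557 = 0.34 |
| Lipids, 38 | 0.934 × 0.866 = 0.81 | 0.934 × 0.714 = 0.67 |
| Three follow-ups, 38 | 0.934 × 0.645 = 0.60 | 0.934 × 0.557 = 0.52 |

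At 88, power at 0.5 SD is 76% (r = 0.5) or 90% (r = 0.7) for lipids, and 95% to 99% with three follow-ups. No cell reaches 0.2.

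The correlation that would give 80% power for lipids is √(1 − (d/d₀)²), with d₀ the unadjusted detectable size. At 38 this is √(1 − (0.5/0.934)²) = 0.85 (0.845 before rounding) for 0.5 SD, and 0.98 for 0.2 SD. At 88 it is 0.56 and 0.94. With three follow-ups at 38, 0.5 SD requires (1 + 2r)/3 − r² = (0.5/0.934)² = 0.287, so r is about 0.73.

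**Step 4: the change-over-time reading.** For within-person change pooled over arms, the detectable change is 0.30 SD of change at 88 and 0.47 at 38. In outcome SDs at r = 0.7, multiply by √(2 × 0.3) = 0.775, giving 0.23 and 0.36. This is not a supplement effect.

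**Step 5: what a null result would leave open at 38.** The 95% CI half-width is 2.028 × √(2/19) = 0.66 SD. For lipids with baseline adjustment it is 0.658 × 0.866 = 0.57 (r = 0.5) or 0.658 × 0.714 = 0.47 (r = 0.7).

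**Step 6: starters only.** With 38 enrolled, the best case is that all are starters, 19 vs 19, which gives 0.93. The stated 0.86 cannot be reached.

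**The case against.** The best defence is that the sentence concerns change over time under a longitudinal model, whereas 0.6 and 0.86 are two-group comparisons at one time. Much of this stands. At 88, the model brings moderate arm differences largely within reach at plausible correlations, and pooled change is detectable at 0.23 outcome SD if r = 0.7. A reader might infer that the SAP's own figures contradict the sentence for every comparison of arms. They do not: the 88-player rows for three follow-ups, and for lipids at r = 0.7, lie between 0.2 and 0.5. The claim is unsupported; it is not contradicted throughout.

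Second, the biomarkers are not itemised. A reader might take it as stated that the sentence covers primary outcomes and that the estimation sentence leaves them out. Neither is stated. The power section places cardiometabolic biomarkers in the exploratory extension, and previously unstudied could mean not studied in the replicated trial. Inclusion of the lipid panel, TNF-a and IL-6 is a reasonable inference, because they are among the non-NFL outcomes the SAP plans to analyse.

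Third, 38 is what recruitment yielded, not an arithmetic error in a plan written around 88. That is right, and the lack of support for small effects does not depend on it.

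Fourth, the effect sizes quoted from the replicated trial, 0.88 to 2.07, are described as starter against non-starter differences. A reader might infer that the statement that 0.86 is well below the reported differences is wrong for supplement against placebo. The documents do not settle this: the statement follows a supplement and placebo comparison in starters, and the cited trial may report suitable values.

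**Conclusion.** The phrase claims a power property that the SAP does not demonstrate. For supplement against placebo, small effects (0.2 SD) are out of reach at 88 and at 38 under every correlation assumed here. Moderate effects (0.5 SD) are largely reachable at 88 with the mixed model. At 38 they are not, unless the correlation is about 0.85 for lipids or about 0.73 for markers with three follow-ups. The unadjusted detectable difference at 38 is 0.93 SD.

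This rests on the conventional meanings of small and moderate, a 19/19 split, no dropout and the assumed correlations. Dropout or a multiplicity adjustment would make the figures less favourable. Only on the pooled-change reading at 88 does the sentence come close to holding, and that reading says nothing about the supplement. The point affects how results are interpreted, not how the trial was run.

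**What to change.** Three changes to the SAP's power section:

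(a) Delete the phrase, or replace it with the detectable supplement-against-placebo difference for the 38 enrolled: 0.93 SD unadjusted. Any adjusted figures should be labelled as depending on an assumed correlation.

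(b) State that the lipid panel, TNF-a and IL-6 are reported as arm differences with 95% confidence intervals, and that a non-significant result is not evidence against a small or moderate effect.

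(c) Note that 0.6 and 0.86 refer to the potential 88 players, name the contrast behind each, and state that 0.86 cannot be reached with 38.

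The cost is text only: no new data, no design change, and outcomes and a model that are already planned. The downside is that the stated power becomes less favourable. Since enrolment is complete, the revised text should be dated as written after it.

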#### **Data analysis**

REDCap provides easy data storage and manipulation (with audit trails for reporting, monitoring and querying patient records), and an automated export mechanism to common statistical packages. We will conduct most analyses using R and relevant R packages (e.g., ggplot2, dplyr, MetaboAnalyst).

This study will collect multiple types of data from each player at multiple time points. Many analyses will be exploratory in nature as this will be the first data of its kind.

#### Continuous outcome measures include:

- Biomarkers NFL
- Cardiometabolic markers TNF-a, IL-6
- Lipid panel TG, HDL-C, LDL-C
- GC-FID for both RBC and Plasma results in 23 free fatty acids concentrations

For these continuous outcomes, we will use a longitudinal mixed-effects model framework to look at both individual and group-level changes from baseline over time. Outcome measures will be transformed where appropriate (e.g., log, sqrt, Box-Cox). Covariates will include age, position, genotypes, treatment, and starter/non-starter, as well as a treatment x starter/non-starter interaction. We will also graphically explore the trajectories of the different biomarkers over time.

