### Untargeted lipidomics will generate data on ~800 lipids

We will analyze the lipidomics data using a custom analysis pipeline developed by the [name] lab based around the MetaboAnalyst R package and custom scripts that is already in use in other metabolomics/lipidomics analyses. Data will be transformed and normalized as appropriate. We will model changes over time in a longitudinal mixed-effects model framework similar to the other biomarkers. We will also use several ordination strategies to determine how lipid species relate to omega-3 supplementation including principal components analysis (PCA), and partial least squares discriminant analysis (PLS-DA). Due to the compositional nature of untargeted lipidomics data, we will use additive log ratio transformed data in the linear models, and use the centered log-ratio transform before performing ordination analyses. We will also further explore the covariance structure of the data and determine which groups of lipid molecules are changing together or in opposing directions. We will then map lipid species to biochemical pathways to gain additional insight into the underlying biology of brain injury and recovery.

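### The SAP's model for NfL and the other continuous outcomes lists no visit, treatment-by-visit or baseline term, and no primary NfL visit or contrast is named

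*SAP*

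**What the plan says.** The SAP, under Continuous outcome measures, sets out a "longitudinal mixed-effects model framework to look at both individual and group-level changes from baseline over time". The terms follow: "Covariates will include age, position, genotypes, treatment, and starter/non-starter, as well as a treatment x starter/non-starter interaction". The only other mention of time in that section is graphical exploration of trajectories. The section on untargeted lipidomics carries the approach to about 800 lipids: "We will model changes over time in a longitudinal mixed-effects model framework similar to the other biomarkers".

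The SAP's power section gives the main aim: "our primary hypothesis-driven question is whether DHA+EPA supplementation will have a protective or restorative effect based on measured levels of markers of neuronal damage", and whether this varies by starter status. Its effect size d "is the difference in the group means divided by the pooled standard deviation", with no visit attached.

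Protocol 9.1.3 says the blood biomarkers "will be measured at baseline, mid-treatment, post treatment, and one month (recovery) after the end of treatment and the football season", which makes four visits. Protocol 7.4 puts the follow-up visit at week 32, seven weeks after the last dose. The lipid panel has two visits, baseline and end of treatment (Protocol 9.2.3). Neither document says which NfL visit or contrast is primary, or whether baseline is an outcome row, is subtracted, or is a covariate.

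**The concern.** In a repeated-measures model, a treatment main effect without treatment-by-visit is a weighted average of the arm differences over all the rows in the model. If baseline is one of those rows, the average includes a visit where randomisation makes the expected difference zero, and the estimate is pulled towards zero. If change scores are used instead, the NfL coefficient averages mid-treatment, end-of-treatment and off-treatment visits. If treatment-by-visit is meant, there are three post-baseline NfL contrasts and none is named.

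The listed interaction adds a further ambiguity. Under 0/1 coding of starter status, the coefficient labelled treatment is the effect in one starter group only, and neither a coding nor an averaged effect is stated.

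Two analysts could therefore follow the same text on the same 38 players and report different treatment effects. The choice of visit and baseline handling could also be made after the data were seen. The SAP's remark that many analyses are exploratory does not cover this, because it presents the neuronal-damage markers as its hypothesis-driven question.

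**Working it through.** **1. The SAP's own power figures.** Two-sample t, two-sided 5% (sidedness is not stated; these figures fit two-sided). Noncentrality = d / √(2/n).
- 44 v 44, d = 0.6: 0.6/0.2132 = 2.81, power 79.5%.
- 22 v 22, d = 0.86: 0.86/0.3015 = 2.85, power 79.6%.

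Both agree with 80%. They reproduce as a single comparison of two means, which does not show which coefficient of the longitudinal model is to be tested.

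**2. What the treatment coefficient targets under the listed terms.** With arm-difference profile δ over the visits and working covariance V, the coefficient targets 1′V⁻¹δ / 1′V⁻¹1. Under compound symmetry this is the plain mean of δ over the rows. Scale the week-25 effect to 1.

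Lipids (baseline, week 25), baseline as an outcome row: (0 + 1)/2 = 50%. As a change score: 100%.

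NfL (baseline / mid / week 25 / recovery). The profiles are assumptions; the documents give none.

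| Profile | Baseline as a row | Change scores |
|---|---|---|
| 0 / 0.5 / 1 / 0 | 1.5/4 = 37.5% | 1.5/3 = 50% |
| 0 / 0.5 / 1 / 0.5 | 2/4 = 50% | 2/3 = 67% |
| 0 / 1 / 1 / 1 | 3/4 = 75% | 3/3 = 100% |

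The pull is not always downwards: 0/1/1/1.5 gives 3.5/3 = 117% with change scores. Under AR(1), with an assumed correlation of 0.5 to 0.8 per 12.5 weeks and the mid visit placed at week 12.5, the baseline-as-a-row shares for the three tabled profiles are 11–23%, 32–39% and 57–64%. Treatment-by-visit with equal baseline means recovers 100% at week 25 for every profile.

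**3. Precision at week 25.** With unit SD and baseline correlation ρ, the per-player variance is 1 unadjusted, 2(1−ρ) for a change score and 1−ρ² with baseline adjustment.
- ρ = 0.7: 1, 0.60 and 0.51.
- ρ = 0.5: 1, 1.00 and 0.75.

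**4. Power at week 25, d = 0.86.** The correlations are assumed, data are complete, and age, position and genotype are ignored. Adjusted noncentrality = unadjusted / √(1−ρ²).

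| Per arm | Unadjusted | Adjusted, ρ = 0.7 | Adjusted, ρ = 0.5 |
|---|---|---|---|
| 22 (SAP, starters only) | 2.85 → 80% | 2.85/0.714 = 3.99 → about 97% | 2.85/0.866 = 3.29 → about 89% |
| 19 (38 enrolled, 1:1) | 0.86/0.3244 = 2.65 → 73% | 2.65/0.714 = 3.71 → about 95% | 2.65/0.866 = 3.06 → about 84% |

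**The case against.** The strongest reply is that the covariate list was never meant to be the whole model. The sentence before it makes change from baseline over time the target, and a list of what covariates will include is not exhaustive. Reading the SAP as dropping time while keeping baseline as an outcome row is the least natural reading, and it produces the lowest shares above. This stands: a reader might infer that time will be omitted, and the documents do not show that. It does not close the gap. The SAP writes out one treatment interaction, with starter status, and omits the one that a question about change needs. Even with treatment-by-visit assumed, the primary NfL contrast is unnamed.

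Three other inferences go too far.
- A reader might say that the model cannot estimate what the study was powered for. But d has no visit attached, so week 25 is a reasonable target and not a documented one.
- The SAP reports the earlier study's placebo starters as "levels more than doubling over the season, while starters on supplementation saw a more modest increase of 35% by the end of the season". Turning these within-arm changes into a treatment difference at season end needs equal baselines in that study, which the SAP does not give.
- A multiplicity charge would need three separate tests at 5%, and neither document proposes them.

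It is also fair that a pooled contrast can be the better choice. If the effect is constant after baseline, a baseline-adjusted post-baseline average has more power than week 25 alone.

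**Conclusion.** The concern holds as under-specification with a concrete and nearly free improvement. The listed terms omit visit, treatment-by-visit and baseline, and neither document names the primary NfL visit or contrast. Fitted as listed with baseline as an outcome row, the treatment coefficient targets 50% of the week-25 lipid effect with equal visit weights, and 37.5% to 75% of the NfL effect for the three tabled profiles under compound symmetry. Change scores remove the lipid problem but leave NfL pooled across on- and off-treatment visits.

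The NfL shares rest on assumed profiles and covariance, and the powers on assumed correlations with the other covariates ignored. They are illustrations and not bounds. The power gain from baseline adjustment would be smaller once age, eight position groups and genotypes are fitted in 38 players. The SAP's power arithmetic is not in dispute. This should be fixed; confidence is medium because the intended model may be better than the written one.

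**What to change.** In the SAP's section on continuous outcomes:
- Keep starter status and position, which are the randomisation factors, and keep treatment-by-starter.
- Add visit as a factor, treatment-by-visit and treatment-by-starter-by-visit. Without the last term, the starter difference is averaged over visits in the same way as the main effect.
- Constrain baseline means to be equal between arms, or enter baseline as a covariate, and state the covariance structure.
- Name one primary NfL contrast: for example supplement minus placebo at end of treatment, averaged over starter groups, or a baseline-adjusted post-baseline average.
- Report the recovery visit as a separate contrast, and the starter difference at the primary visit with a confidence interval.
- Use the same terms for the lipidomics models.
- Because Protocol 2.2 records the study as completed, disclose whether the contrast was fixed before unblinding.

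**Cost.** SAP wording and a few lines of code; no new data. There are a few more parameters to estimate in 38 players. If the effect is constant after baseline, week 25 alone loses some power: about 97%/89% against 99.9%/99% for the adjusted average (22 per arm, d = 0.86, ρ = 0.7/0.5). A contrast named now may have to be reported as post hoc.

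The starter difference stays imprecise. With an assumed even split of the 38 into four cells of 9.5, the unadjusted SE is √(4/9.5) = 0.65 SD, and 80% power needs about 0.65 × 2.88 = 1.9 SD, or about 1.3 SD with baseline adjustment at ρ = 0.7.
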